### 7.6.4 Post-Treatment Visits/Safety Follow-Up Visit

The mandatory Safety Follow-Up Visit should be conducted approximately 30 days after the last dose of trial treatment or before the initiation of a new anti-cancer treatment, whichever comes first. All AEs that occur prior to the Safety Follow-Up Visit should be recorded. Subjects with an AE of Grade > 1 that is at least possibly attributed to study treatment will be followed until the resolution of the AE to Grade 0-1 or until the beginning of a new anti-neoplastic therapy, whichever occurs first. SAEs that occur within 90 days of the end of treatment or before initiation of a new anti-cancer treatment should also be followed and recorded.

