## 8.2 Pembrolizumab

Adverse events (both non-serious and serious) associated with pembrolizumab exposure may represent an immunologic etiology. These adverse events may occur shortly after the first dose or several months after the last dose of treatment. Pembrolizumab must be withheld for drug-related toxicities and severe or life-threatening AEs as per below. It will be up to investigator to determine if each AE is attributed to metformin (and follow guidelines above) or pembrolizumab to follow guidelines below.

Pembrolizumab administration should be delayed for the following:

- Any Grade  $\geq 2$  non-skin, drug-related adverse event, with the following exceptions:
  - Grade 2 drug-related fatigue or laboratory abnormalities do not require a treatment delay
- Any Grade 3 skin, drug-related adverse event
- Any Grade 3 drug-related laboratory abnormality, with the following exceptions:
  - Grade 3 amylase or lipase abnormalities that are not associated with symptoms or clinical manifestations of pancreatitis do not require a dose delay.
  - If a subject has a baseline AST, ALT, or total bilirubin that is within normal limits, delay dosing for drug-related Grade  $\geq 2$  toxicity

- If a subject has baseline AST, ALT, or total bilirubin within the Grade 1 toxicity range, delay dosing for drug-related Grade  $\geq 3$  toxicity
- Any adverse event, laboratory abnormality, or intercurrent illness, which, in the judgment of the investigator, warrants delaying the dose of study medication

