### **11.4 Adverse Event Collection and Reporting**

The collection of non-serious AE information should begin at initiation of study drug, all events prior to that time should be documented as medical history (BUT all SAEs must be collected from consent, see Section 11.3). All adverse events (not just those deemed to be treatment-related) should be collected continuously during the treatment period and for a minimum of 90 days following the last dose of study treatment.

Adverse events must be collected using institutional adverse event logs and captured in REDCap.

AEs should be followed to resolution or stabilization, or reported as SAEs if they become serious. Follow-up is also required for AEs that cause interruption or discontinuation of study drug and for those present at the end of study treatment as appropriate. Subjects with an AE of Grade > 1 that is at least possibly attributed to study treatment will be followed until the resolution of the AE to Grade 0-1 or until the beginning of a new anti-neoplastic therapy, whichever occurs first. SAEs that occur within 90 days of the end of treatment or before initiation of a new anti-cancer treatment should also be followed and recorded through resolution.

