## STUDY CALENDAR

Cycle	Screening	Lead in Treatment Before Cycle 1			1	2	3, 5, 7, 9 etc.	4, 6, 8, 10, etc.	Off Study / Safety follow-up (30 days post tx) i	Survival Follow-up
Day	28 days before 1st lead-in tx o	-21 c	-14	-7	1	1	1	1		
Window (days)				+/-1 day	+/-1 day	+/-3 days	+/-3 days	+/-3 days	+/-3 days	+/-4 weeks
Arm 1										
Metformin ER daily			X a	X b	X	X	X	X		
Pembrolizumab q 3 weeks or q 6 weeks a					X	X	X	X		
Correlative blood draws h			X h		X	X				
Arm 2										
Metformin ER daily				X a	X b	X	X	X		
Pembrolizumab q 3 weeks or q 6 weeks p		X			X	X	X	X		
Correlative blood draws h		X h		X		X				
Both Arms										
Informed consent	X									
Demographics	X									
Medical history	X									
Concomitant meds	X	X	X-----X							
Physical exam d	X	X	X	X	X		X		X	
Vital signs	X	X	X	X	X	X	X	X	X	
Height	X									
Weight	X	X	X	X	X	X	X	X	X	
Performance status	X k	X	X	X	X	X	X		X	
CBC w/diff, plts f	X k	X	X	X	X	X	X	X	X	
Serum chemistry f	X k	X	X	X	X	X	X	X	X	
Urinalysis	X k				X		X			
Coagulation tests	X k				X		X			
C-peptide	X k				X	X				
Thyroid Tests k	X k				X		X			
Vitamin B-12	X k				X	X				
Lactate (Lactic Acid)	X k				X	X				
Adverse event evaluation m		X-----X								
Pregnancy test e				X						
Radiologic evaluation l, q	X						X			
Correlative biopsy g	X					X				
Medication diary n	X		X	X	X	X	X	X		
Post-tx survival status j									X	X
a. Metformin ER starting dose 1000mg daily b. Metformin ER escalation dose 2000mg daily										

Cycle	Screening	Lead in Treatment Before Cycle 1			1	2	3, 5, 7, 9 etc.	4, 6, 8, 10, etc.	Off Study / Safety follow-up (30 days post tx) i	Survival Follow-up
Day	28 days before 1st lead-in tx o	-21 c	-14	-7	1	1	1	1		
Window (days)				+/-1 day	+/-1 day	+/-3 days	+/-3 days	+/-3 days	+/-3 days	+/-4 weeks

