
c. Only applies to Arm 2 as Arm 1 does not have a D -21.
 
d. Full physical exam at screening, directed on other visits
 
e. Child-bearing females only. Test within 72 hours of first treatment (See 7.6.1)
 
f. See table 1 in section 7.5.7
 
g. Archival acceptable at screening; Cycle 2 repeat biopsy if clinically feasible. Biopsy may be of a target or non-target lesion but if there is only one target lesion that is being followed, this lesion should be avoided for biopsy unless discussed with PI.
 
h. 60mls in EDTA tubes and 5mls in red top serum tube at Day -14 (Arm 1) or Day -21 (Arm 2); and also collect Day 1 (Arm 1) or Day -7 (Arm 2); and also collect Cycle 2 Day 1 (week 4). The Day -14 & Day -21 respective samples must be collected before any study treatment is given on those days – if this pre-treatment sample is missed then no other blood correlatives should be collected for those subjects. This first pre-treatment correlative blood sample may be obtained at another time-point after randomization but prior to first lead in treatment with the PI's approval.
 
i. Should be completed at 30 days post-treatment OR before new anti-cancer therapy whichever occurs first.
 
j. Every 3 months/12 weeks - can be completed by telephone
 
k. ECOG PS and screening laboratory tests to be completed within 10 days of first tx (may be performed on day 1 prior to tx)
 
l. Scans to be performed every 12 weeks +/- 5 days starting with C3D1
 
m. Adverse events should be collected for 90 days following the last dose of study treatment
 
n. Subjects will be provided with a medication diary at screening but will not complete entries until dispensed Metformin. The medication diary will be returned to research staff and a new diary issued at the end of each course.
 
o. Subjects are randomized to either Arm 1 or Arm 2 after registration (eligibility is confirmed). These arms are independent of each other. Each arm has the same amount of time 28 days, to complete screening activities before their respective first lead in treatment visits (Day -21 or Day -14).
 
p. Pembrolizumab may be given at 200mg q3 weeks or 400mg q6 weeks and may be changed during course of treatment per investigator discretion.
 
q. Temporarily discontinuing metformin in patients undergoing radiologic studies in which intravascular iodinated contrast media are utilized is left up to investigator discretion.
										

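### For non-serious adverse events, Section 7.6.4 sets recording up to the safety visit at about Day 30, while Section 11.4 and calendar footnote m require 90 days, and no contact is named for finding new events in between

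*Combined protocol and SAP*

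**What the plan says.** Section 7.6.4 fixes the visit: "The mandatory Safety Follow-Up Visit should be conducted approximately 30 days after the last dose of trial treatment", or before new anti-cancer treatment if that is sooner. It then gives the rule for adverse events in general: "All AEs that occur prior to the Safety Follow-Up Visit should be recorded". The same paragraph gives serious events a longer rule of their own, covering "SAEs that occur within 90 days of the end of treatment or before initiation of a new anti-cancer treatment".

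Section 11.4 says that all adverse events, related or not, "should be collected continuously during the treatment period and for a minimum of 90 days following the last dose of study treatment". It repeats the 90-day rule for serious events. Footnote m, attached to the adverse event row of the Study Calendar, reads: "Adverse events should be collected for 90 days following the last dose of study treatment".

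Section 7.5.1 has events assessed on the calendar's schedule and refers the reader to Section 11 for how to record them. Section 7.6.5 and footnote j describe the only contacts after the safety visit: about every 12 weeks, by telephone if wished, to establish survival status.

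**The concern.** Adverse events graded by CTCAE are a secondary endpoint. Section 10.1 summarises them as the number and percentage of patients with each toxicity. Section 8.2 says of pembrolizumab toxicity: "These adverse events may occur shortly after the first dose or several months after the last dose of treatment". The period after Day 30 is therefore one in which the protocol itself expects events. Section 3.3 adds that earlier safety data for the combination came from lower metformin doses than the 2000 mg used here, so the toxicity description is a main product of the trial.

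Staff who follow 7.6.4 would stop looking for new non-serious events at the safety visit. Staff who follow 11.4 would continue to Day 90, but the calendar names no occasion on which to ask. Under either reading, late non-serious immune events can go unrecorded, and the reported percentages could rest on a shorter window than the one stated in 11.4.

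**Working it through.** The plan gives no figure to reproduce. The check sets the rules side by side and counts days.

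**1. Recording windows after the last dose**

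| Source | Non-serious events | Serious events |
|---|---|---|
| 7.6.4 | up to the safety visit, about Day 30 or earlier | 90 days, or before new treatment |
| 11.4 | at least 90 days | 90 days, or before new treatment |
| Calendar footnote m | 90 days | 90 days (no distinction made) |

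The windows disagree only in the non-serious column. Section 7.6.4 does not expressly say that recording stops at the visit. That is still its natural reading, because the same paragraph grants a longer window to serious events alone.

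**2. Length of the mismatch**

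- Visit on Day 30: 90 − 30 = 60 days, and 60/90 = two thirds of the window.
- With the calendar's ±3 days on that visit (Day 27 to 33): 90 − 33 = 57 to 90 − 27 = 63 days.
- If new treatment brings the visit forward to Day d, the mismatch is 90 − d, which exceeds 60 whenever d is below 30.

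**3. Scheduled contacts between the safety visit and Day 90**

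The calendar has no visit column between the 30-day visit and survival follow-up. Sections 7.6.4 and 11.4 require events already open to be followed, but set no dated contact for detecting new ones.

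The survival contact is due at 12 ± 4 weeks:

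- nominal: 12 × 7 = 84 days
- earliest: 8 × 7 = 56 days
- latest: 16 × 7 = 112 days

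Counting from the last dose is an assumption. Section 7.6.5 starts survival follow-up at confirmed progression or new therapy, while 7.10 refers to removal from treatment. On this assumption the nominal contact falls 90 − 84 = 6 days before Day 90, and the permitted range lies on both sides of it. The contact as scheduled does not reliably close the window, and adverse events are not among its stated purposes.

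**4. New anti-cancer therapy**

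The all-event sentence in 11.4 has no cutoff at new therapy. The serious-event sentence in both sections joins the 90-day limit and the start of new therapy with an *or* and does not say which governs. On one reading, non-serious events would be collected after new therapy starts while serious events would not.

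**5. Weight of one event**

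If all 25 planned patients are treated, one patient is 1/25 = 4 percentage points in a toxicity table.

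**The case against.** The strongest reply is that the protocol already says which section governs. Section 7.5.1 sends readers to Section 11 for recording adverse events, 11.4 is explicit about 90 days, and footnote m puts 90 days on the calendar's own adverse event row. A site that follows 11.4 also meets 7.6.4, since recording more than 7.6.4 asks breaks no rule. Related events above Grade 1 are followed until they settle or new therapy starts. The safety summary is descriptive, the dose-limiting toxicity rule covers only the lead-in and the first 28 days of combination treatment, and the primary endpoint is response.

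Much of this stands, and it limits the point. It does not remove it. Nothing says that 11.4 overrides 7.6.4, and 7.5.1 also ties assessment to a calendar that has no visit after Day 30 for finding new events. Following an open event does not detect a new one.

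A reader might infer three stronger things that the documents do not support:

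- **Serious late immune events fall outside the window in 7.6.4.** They do not: serious events have a 90-day window there as well as in 11.4. The lack of a named contact could still delay their detection.
- **Sites will record unevenly.** This is plausible where several sites work from one protocol with two rules. It is an inference, and Section 14.3.1 provides for central data review and study monitoring.
- **Two thirds of late events will be lost.** The 60 days measure an interval without a named contact, not missing data.

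**Conclusion.** The inconsistency is real and limited to non-serious adverse events: about Day 30 in 7.6.4 against 90 days in 11.4 and footnote m, a difference of about 60 days. Separately, the calendar names no contact for finding new events of any kind between the 30-day visit and Day 90. Together these may lead to under-recording of late non-serious immune events in a secondary endpoint. The direction of any error is towards understating late toxicity; its size cannot be derived from the documents.

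The conclusion rests on reading 7.6.4 as closing the non-serious window at the visit, and on the calendar columns as they appear in the text available. The right-hand end of the adverse event bar is not legible there, but a longer bar would not add a visit. The point should be corrected because the remedy is nearly free. It does not threaten the primary analysis or the stopping rule.

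**What to change.** 1. Align the all-event sentence in 7.6.4 with the 90-day window of 11.4 and footnote m.
2. Name in the Study Calendar a contact at or after Day 90, by telephone if preferred, to ask about new events. Alternatively, have the first survival contact on or after Day 90 ask retrospectively about serious and non-serious events through Day 90. Simply adding questions to the first 12-week call is not enough, because that call may come before Day 90.
3. State one rule, the same for serious and non-serious events, on whether collection continues after new anti-cancer therapy starts. Use it in both 7.6.4 and 11.4.

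The cost is wording changes and a few questions on a call.

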### 7.6.5 Survival Follow-up

Once a subject experiences confirmed progression or starts a new anti-cancer therapy, the subject moves into the survival follow-up phase and should be contacted by telephone or seen in clinic every 12 weeks +/- 4 weeks to assess for survival status until death, withdrawal of consent, or at the end of the study, whichever occurs first. Patients will be followed up to 5 years.

## 7.7 Definition of Dose-Limiting Toxicity

### 7.7.1 Lead-in Safety Analysis

The first nine patients will be enrolled as the lead-in population. Safety analysis will be performed with this population and will be analyzed on a rolling basis. Monthly review with all active sites will be held to determine if any of these first 9 patients have experienced a dose limiting toxicity, DLT, (described below) to evaluate the safety of the combination. Safety analysis will be considered complete after the ninth patient has completed 28 days of combination treatment. Patients will continue to be enrolled past the initial safety cohort, but if at any time, safety analysis reveals >3 out of the 9 patients in the safety cohort have developed a DLT, then no further patients may be enrolled due to excess toxicity with this combination.

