### 7.7.2 Dose Limiting Toxicity

Dose limiting toxicity (DLT) is defined as the appearance of side effects during treatment that are attributed to treatment and severe enough to prevent continuation of treatment or grade 3 or 4 non-hematologic toxicities other than alopecia, nausea or vomiting and that in the case of pembrolizumab, do not resolve with steroids after four weeks. If more than three of nine patients develop a DLT, then combination will be considered unsafe and the study will not proceed. Patients are assessed for DLTs during the lead-in period as well as for the first 28 days of combination treatment.

Management and dose modifications associated with the above adverse events are outlined in Section 8.

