### 8.2.5 Management of Infusion Reactions:

Since pembrolizumab contains only human immunoglobulin protein sequences, it is unlikely to be immunogenic and induce infusion or hypersensitivity reactions. However, if such a reaction were to occur, it might manifest with fever, chills, rigors, headache, rash, pruritus, arthralgias, hypo or hypertension, bronchospasm, or other symptoms. All Grade 3 or 4 infusion reactions should be reported within 24 hours to University of Cincinnati PI (coordinating center), as well as to the local PI and reported as an SAE if criteria are met. Infusion reactions should be graded according to NCI CTCAE (version 5.0) guidelines.

Treatment recommendations are provided below and may be modified based on local treatment standards and guidelines as appropriate:

**For Grade 1 symptoms:** (Mild reaction; infusion interruption not indicated; intervention not indicated)

Remain at bedside and monitor subject until recovery from symptoms. The following prophylactic premedications are recommended for future infusions: diphenhydramine 25-50 mg (or equivalent) and/or acetaminophen 325 to 1000 mg at least 30 minutes before additional pembrolizumab administrations. A H1 blocker may also be administered.

**For Grade 2 symptoms:** (Moderate reaction requires therapy or infusion interruption but responds promptly to symptomatic treatment [e.g., antihistamines, non-steroidal anti-inflammatory drugs, narcotics, corticosteroids, bronchodilators, IV fluids]; prophylactic medications indicated for  $\leq$  24 hours).

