### 10.3 Early Stopping Rules:

In order to verify safety of the combination of metformin and pembrolizumab, an early stopping rule will be used if 3 out of 9 (33%) of the safety lead-in develop DLTs (see definition above). The lead-in will be on a rolling basis but if three patients develop DLTs, the study will be stopped so that safety may be investigated by the DSMB. If DLTs are confirmed, the study will be closed to enrollment due to safety concerns.

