### **11.3 Serious Adverse Event Collection and Reporting**

All Serious Adverse Events (SAEs) that occur following the subject's written consent to participate in the study should be collected on institutional adverse event logs and reported using the applicable FDA MedWatch form within 24 hours of learning of the event to the University of Cincinnati PI and Project Manager and entered into REDCap. Sites should contact the UC Project Manager for copies of the MedWatch form.

SAEs must also be reported to the IRB of record, and/or FDA as needed based on applicable institutional and regulatory timeframes.

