## **STUDY OVERSIGHT AND DATA REPORTING / REGULATORY REQUIREMENTS**

### **14.1 Study Oversight**

This protocol is monitored at several levels, as described in this section. The UC Principal Investigator is responsible for monitoring the conduct and progress of the clinical trial, including the ongoing review of accrual, patient-specific clinical and laboratory data, and routine and serious adverse events reporting. The UC Principal Investigator has access to the data at all times through REDCap. All Study Investigators at participating sites who register/enroll patients to this study are responsible for timely submission of data via REDCap and timely reporting of adverse events to the UC PI and in REDCap.

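### A dose-limiting toxicity that is not serious carries no dated notice to the coordinating PI, so the lead-in stopping count can lag by up to about a month while enrolment stays open

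*Combined protocol and SAP*

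**What the plan says.** Section 7.7.1 makes the first nine patients the safety lead-in. It states the principle, "Safety analysis will be performed with this population and will be analyzed on a rolling basis", and then one concrete procedure: "Monthly review with all active sites will be held to determine if any of these first 9 patients have experienced a dose limiting toxicity". Enrolment does not pause: "Patients will continue to be enrolled past the initial safety cohort, but if at any time, safety analysis reveals >3 out of the 9" with a DLT, enrolment closes. Section 7.7.2 gives the same count: "If more than three of nine patients develop a DLT, then combination will be considered unsafe and the study will not proceed". Section 10.3 gives another: "The lead-in will be on a rolling basis but if three patients develop DLTs, the study will be stopped", so that the DSMB can investigate.

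Section 7.7.2 defines a DLT by grade, or by inability to continue treatment, not by seriousness. Reporting duties, however, follow seriousness:

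- Section 11.3 requires SAEs to reach the coordinating PI and Project Manager "within 24 hours of learning of the event".
- Section 8.2.5 adds one class of event whether or not it is serious: "All Grade 3 or 4 infusion reactions should be reported within 24 hours to University of Cincinnati PI".
- Section 11.4 sends other adverse events to site logs and REDCap and sets no deadline.
- Section 14.1 makes sites responsible for "timely reporting of adverse events to the UC PI and in REDCap", without a number of days. It also gives the coordinating PI ongoing review and constant access to REDCap.

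Under Section 5.1 the coordinating PI confirms eligibility before each registration. The listed steps do not include a check of the DLT count.

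**The concern.** A stopping rule that can act at any moment, with enrolment open, protects patients only if the count behind it is current. Here the event that drives the rule is the DLT, but the event that triggers prompt notice is the SAE. The two overlap without coinciding. A Grade 3 diarrhea attributed to metformin and managed without admission can meet the grade part of the DLT definition, yet need not meet any SAE criterion in Section 11.2. The same holds for a lower-grade effect that prevents continuation.

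The trial has several sites, so one site cannot know of another's DLTs unless they are reported. Section 3.3 gives the reason for the lead-in: safety of the combination has not been documented at this metformin dose. At stake is whether a few patients enter after the point at which the plan itself would have closed enrolment.

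**Working it through.** **1. Which DLTs reach the coordinating PI, and when**

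| Kind of DLT | Route | Deadline |
|---|---|---|
| Meets an SAE criterion (11.2) | 11.3 | 24 hours |
| Grade 3 or 4 infusion reaction, serious or not | 8.2.5 | 24 hours |
| Any other | Logs and REDCap (11.4), general duty (14.1), monthly review (7.7.1) | None stated; the review is the only dated step |

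The third row is the gap.

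**2. The plan's own figure.** Section 10.3 states its threshold as 33%, and 3/9 = 33.3% reproduces it. The count in 7.7.1 and 7.7.2 is more than three, so at least 4/9 = 44.4%. The plan states no figure for review lag or for patients entering after the trigger, so there is none to reproduce.

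**3. Accrual.** Section 10.2 plans 25 patients over 18 to 24 months: 25/24 = 1.04 to 25/18 = 1.39 per month.

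**4. Entries while the count is out of date.** Assume even accrual, a triggering DLT from the third row, and no reading of REDCap for DLTs between reviews. With L = monthly rate × lag in months:

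- Worst case, DLT just after a review (lag 1 month): L = 1.04 to 1.39. With Poisson arrivals, the chance of at least one entry is 1 − e^(−L) = 65% to 75%.
- Average case, DLT equally likely at any time in the month (mean lag ½ month): 1.04/2 = 0.52 to 1.39/2 = 0.69. With L now the full-month value, the chance of at least one entry is 1 − (1 − e^(−L))/L = 38% to 46%. So in 54% to 62% of such cases nobody enters.
- With 24-hour notice (lag 1/30.4 month): 1.04/30.4 = 0.03 to 1.39/30.4 = 0.05, with a 3% to 5% chance of at least one entry.

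**5. Two comparisons for scale.** The DLT observation period is the lead-in (14 or 21 days) plus 28 days, that is 42 to 49 days. Open enrolment admits 1.04 × 42/30.4 = 1.4 to 1.39 × 49/30.4 = 2.2 patients over that period, whatever the review frequency.

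The unresolved threshold also matters more than the lag. Exact binomial chance of reaching the count among nine patients:

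| True DLT rate | At least 3 | At least 4 |
|---|---|---|
| 20% | 26% | 9% |
| 33% | 62% | 34% |
| 40% | 77% | 52% |

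**The case against.** The plan is less dependent on the monthly meeting than a quick reading suggests. Sections 7.7.1 and 10.3 both call the process rolling. The coordinating PI has ongoing review, constant data access and the last word on each registration. Serious DLTs arrive within 24 hours, and the important-medical-event category in 11.2 can take in some events without admission. Some pembrolizumab toxicities also cannot be confirmed as DLTs at once, because 7.7.2 makes their status depend on whether they resolve with steroids over four weeks.

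All of this narrows the point; none of it closes the gap. No one is assigned a running count. REDCap access helps only after the site has entered the event, and entry has no deadline. The steroid clause is a reason to notify suspected DLTs and adjudicate later.

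Three stronger readings do not hold:

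- A reader might infer that DLTs are counted only monthly, so that patients necessarily keep starting the combination after the count is met. The rolling language and the PI's access make this a possibility, not a certainty.
- A reader might add patients already in lead-in to the new registrations and reach a larger number. That mixes two different events. At steady accrual, combination starts in a month equal the accrual rate, 1.0 to 1.4. Section 7.7.1 closes only enrolment, so under its wording lead-in patients would add the second drug even with no lag.
- A reader might argue that, with no visit at Day 28, events surface only at Cycle 3. Adverse events are collected continuously (11.4 and the Study Calendar), so this does not follow.

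**Conclusion.** The point stands as a minor one. A DLT that is neither an SAE nor a Grade 3 or 4 infusion reaction has no dated notification duty and can leave the stopping count out of date for up to about a month. At planned accrual this means about 0.5 to 0.7 further entries on average and 1.0 to 1.4 at worst.

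The figures rest on even accrual, on the triggering DLT being non-serious, and on REDCap not being read for DLTs between reviews. Slower accrual or active reading of REDCap would lower them. The documents do not say whether the nine-patient lead-in is already complete; if it is, the change brings no further benefit in practice.

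Separately, and with more effect on the rule, Sections 7.7.1 and 7.7.2 contradict Section 10.3 both on the count (more than three against three) and on the consequence (closing enrolment against stopping the study). The documents do not settle which governs.

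**What to change.** In Section 7.7.1, require sites to notify the coordinating PI and Project Manager of every suspected DLT in the nine lead-in patients within 24 hours of awareness, through the contact route in 11.3, whether or not the event is serious. Name who keeps a running count of suspected and confirmed DLTs. In Section 5.1, add a check of that count to the existing eligibility confirmation before each registration. Keep the monthly meeting for adjudication, including events whose status depends on the four-week steroid clause.

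The cost is a few sentences, one checklist line and a small number of extra notices for nine patients. The change leaves doses, the DLT definition and the threshold as they are.

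As a separate correction, reconcile 7.7.1 and 7.7.2 with 10.3 on the count and on the consequence, and state what each means for patients already in lead-in when the rule is met.
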